7.0 Risks

Known and expected risks associated with the use of the intervention are the following:

- Allergic reaction to APIS[®] biomaterial
- Surgical site pain, infection, minimal bleeding, oozing, swelling, and/or itching
- Scar
- Loss of confidentiality
- Feeling uncomfortable answering questionnaire

8.0 Reporting of Adverse Events or Unanticipated Problems involving Risk to Participants or Others

Participants will be instructed at the time of consent to contact a member of the study team should they experience any adverse event or unanticipated problem. An on-call

pager number will be provided to study participants. All adverse events and unanticipated problems will be reported to the VUMC IRB in accordance with the VUMC IRB policy. Additionally, all serious adverse events will be reported to the manufacturer of APIS®, SweetBio, Inc (Memphis, TN).

9.0 Study Withdrawal/Discontinuation

Participants have the ability to withdraw or discontinue from the study at any time. Subjects will be instructed to notify a member of the study team if they wish to withdraw, and any data collected for research will be discarded.

Participants enrolled in the study may be terminated from the study at the investigator's discretion including but not limited to the following:

- Lost to follow-up
- Nonadherence with wound care
- A participant's health status changes significantly which makes them not eligible for the study
- Trauma to the post-operative wound

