The novel biomaterial APIS[®] (SweetBio, Inc. Memphis, TN) is an advanced synthesis of gelatin, manuka honey, and hydroxyapatite bioengineered to protect wounds, manage exudate, and maintain a moist environment. It is FDA cleared (FDA number K1827250) for wound management across 9 indications including surgical wounds. It has been used successfully in a small case series of 8 patients for post-operative Mohs surgical wounds on the head and distal lower extremities. Time to complete re-epithelialization was 6 weeks (42 days), suggesting a reduction in healing time compared to standard SIH times for the leg and head of 127 and 57 days, respectively.^{10,11} Use of this novel biomaterial to enhance SIH is hypothesized to reduce healing times when compared to standard SIH wound care. This provides a useful option to aid SIH in sites like the lower legs, where healing can be prolonged due to intrinsic factors (e.g., cardiovascular disease, peripheral vascular disease, diabetes) or extrinsic factors (e.g., increased risk of surgical site infection following dermatologic surgery at sites below the knee).^{10,12}

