2.0 Rationale and Specific Aims

Randomized, comparative studies evaluating augmented SIH compared to conventional SIH in dermatologic surgery are limited. This study aims to evaluate whether use of a novel biomaterial enhances SIH, particularly in shortening time to complete re-epithelialization. Patients undergoing Mohs micrographic surgery amenable to SIH on the head and distal lower extremities will be randomized into one of four groups (standard SIH or biomaterial APIS[®] enhanced SIH on the head or distal lower extremities). Patients will have regularly scheduled follow-up with questionnaires at each visit. We aim to evaluate whether use of this novel biomaterial decreases complete reepithelialization times, reduces infection rates, and improves cosmetic outcomes.

Outcome Measures

Primary:

1. Time to complete re-epithelialization

Patients will be seen in office 14 days post-operative, then every 14 days thereafter until complete re-epithelialization is achieved. Patients will also submit photos via Vanderbilt HIPAA compliant Box at regular follow-up intervals (post-operative day 7 then every 14 days thereafter until complete re-epithelialization is achieved). Time elapsed from surgery date to complete re-epithelialization will be noted in days.

Secondary:

1. Patient and Observer Scar Assessment Scale (POSAS) Patient Scale Score Version 2.0

Patients will complete the POSAS Patient Scale after complete re-epithelialization is achieved. The POSAS Patient Scale is a validated and widely accepted scar assessment tool. The patient scale has six questions assessing scar pain, itch, color, stiffness, thickness, and irregularity rated from 1 (no, not at all/normal skin) to 10 (yes, very much/worst imaginable). Scale from 6-60 with a final seventh question rating patient's overall opinion of scar quality (1-10).

2. Visual Analog Scale (VAS) – Provider Scar Ranking

Digital standardized photographs of scars after complete re-epithelialization is achieved will be assessed by two blinded dermatologists using the VAS. This scale ranges from 0 or normal skin to 10 or worst possible scar taking into account the scar's pigmentation, vascularity, contour, observer comfort, and overall severity. VAS scores of novel biomaterial will be compared to standard SIH.

3. Size of wound

Post-operative wounds will be measured at regularly scheduled follow-ups. The area and volume for each patient's wound will be calculated.

4. Pain score

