Subsequent Post-operative Visits – Post operative Day 14 then every 14 days thereafter until complete re-epithelialization is achieved. Patients enrolled in study will be provided a brief questionnaire to complete at in-person office follow-up visits. Post-operative wounds will be assessed for any complications. Size of wounds in addition to photographs will be obtained until complete re-epithelialization is achieved. Patients will also upload post-operative photos to Vanderbilt's HIPAA compliant Box post-operative day 7 then every 14 days thereafter until complete re-epithelialization is complete.

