10.0 Statistical Considerations

The primary endpoint is time to achieve complete re-epithelialization. The mean number of days required to achieve complete re-epithelialization between control and experimental groups will be analyzed with a Student's T-test. The null hypothesis is that there is no statistically significant difference between control and experimental complete re-epithelialization times. Secondary outcomes of patient and observer cosmetic outcome will be compared similarly.

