11.0 Privacy/Confidentiality Issues

All data will be secured, and confidentiality will be upheld by all members of the research team. Participants will be assigned a study identification code in order to deidentify the study data. A crosslink will exist to link study identification codes to participant identifiers. This crosslink will only be accessible to a limited number of IRB trained and approved study personnel. Study data will be contained in a password protected Excel spreadsheet and stored on the Vanderbilt HIPAA compliant Box. Patients enrolled in this study may request to have all data removed/destroyed from the database if they elect to withdraw from the study.

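### Sections 9.0 and 11.0 give different rules for the data of participants who withdraw, and section 9.0 as written discards randomised patients' safety, wound and follow-up data; the primary t-test omits those who leave before healing under either rule.

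*Combined protocol and SAP*

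**What the plan says.** Section 9.0 allows withdrawal at any time and asks participants to tell the study team "if they wish to withdraw, and any data collected for research will be discarded". It makes no exception for data already collected and requires no request from the patient. Section 11.0, on the same event, says that enrolled patients "may request to have all data removed/destroyed from the database if they elect to withdraw from the study".

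Section 9.0 also lets the investigator remove people: participants "may be terminated from the study at the investigator's discretion including but not limited to the following", followed by loss to follow-up, nonadherence, changed health status and wound trauma. No data rule is attached to this second route.

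The primary analysis in section 10.0 compares "The mean number of days required to achieve complete re-epithelialization between control and experimental groups" by Student's t-test, and the cosmetic outcomes are handled in the same way. That section defines no analysis population, censoring rule or method for missing data.

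Visits in section 6.0 run "Post operative Day 14 then every 14 days thereafter until complete re-epithelialization is achieved". Wound size, pain, infection, bleeding and ease of care are collected at follow-up along the way (section 2.0). The two scar scores come only after healing.

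**The concern.** Two staff members could each follow the protocol and treat the same withdrawn patient differently, one deleting the record and the other keeping it. Deletion cannot be undone.

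The data at risk bear on stated objectives. Section 2.0 asks whether the biomaterial "reduces infection rates, and improves cosmetic outcomes", and an infection recorded before withdrawal would leave the arm counts. Withdrawal occurs after randomisation and could depend on arm or on healing. No sham is described in section 6.0, and the only assessors stated to be blinded are those of the photographs, which "will be assessed by two blinded dermatologists using the VAS". Slow healers also carry the longest run of visits. If loss differs by arm and is related to outcome, the patients analysed are no longer the groups that were randomised.

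**Working it through.** **Step 1. The two rules side by side.** Both sentences concern withdrawal by the participant. Section 9.0: trigger is withdrawal, result is discard, no condition. Section 11.0: trigger is withdrawal plus a request, result is removal. For a patient who withdraws and asks for nothing, section 9.0 discards the data and section 11.0 implies that they stay. Nothing in section 10.0 decides between them.

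**Step 2. What the discard rule itself costs.**

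| Data | Withdraws before healing | Withdraws after healing |
|---|---|---|
| Healing date (primary) | Never observed; omitted from the t-test under either rule | Observed, then lost if discarded |
| Patient and photograph scar scores | Not yet collected | Lost if already collected |
| Infection, bleeding, pain, wound size, ease of care | Lost if discarded | Lost if discarded |
| Follow-up time without healing | Lost if discarded; needed for censoring | Not applicable |

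For those who leave before healing, retention alone changes the planned primary estimate by 0 days.

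**Step 3. Size of the complete-case bias (illustration).** The documents give no withdrawal rate, SD or effect size, so there is no plan figure to reproduce.

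- From the documents: 20 head and 20 leg patients per arm (section 6.0), and "standard SIH times for the leg and head of 127 and 57 days, respectively" (section 1.0), used here as means in both arms.
- Assumed: no true effect; lognormal times with CV 0.5 (range 0.4 to 0.7); loss at random from the slower half within each site, split equally between sites.
- Simulation: 10,000 trials per scenario at CV 0.5, and 6,000 at CV 0.4 and 0.7.

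Hand check at CV 0.5: s = sqrt(ln(1 + 0.5²)) = 0.472 and Φ(s) = 0.682. The slower half averages 2Φ(s) = 1.363 times the mean, and the faster half 0.637 times.

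- Lose 4 of 40 (2 of the 10 slower per site): (10×0.637 + 8×1.363)/18 = 0.960, a shift of -4.0%. On the site average (57 + 127)/2 = 92 days this is about -3.7 days.
- Lose 8 of 40 (4 of 10 per site): (10×0.637 + 6×1.363)/16 = 0.909, a shift of -9.1%, or about -8.4 days.

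The simulation, which splits each sample at its own median, gives slightly smaller shifts:

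| Lost per arm (of 40) | Complete-case t-test, shift in days | False positives | Retained and censored, shift in days |
|---|---|---|---|
| 0 v 0 | 0.0 | 1.3% | not reported |
| 4 v 0 | -3.6 | 1.7% | -1.3 |
| 8 v 0 | -8.0 | 3.2% | -2.8 |
| 8 v 2 | -6.4 | 2.1% | -2.3 |
| 4 v 4 | -0.2 | 1.1% | not reported |
| 8 v 8 | -0.1 | 0.7% | not reported |

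The shift is the arm with more loss minus the other. With an SD of the difference of 11.1 days, 4 v 0 is 3.6/11.1 = 0.32 of a standard error and 8 v 0 is 8.0/11.1 = 0.72. Over CV 0.4 to 0.7 the shift runs from -2.9 to -4.6 (4 v 0) and from -6.6 to -10.6 (8 v 0). The highest pooled false-positive rate is 4.9% (8 v 0, CV 0.7).

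**Step 4. What each change contributes.** The last column takes withdrawal as uniform between surgery and healing, censors at the last completed 14-day visit, and averages Kaplan-Meier means over sites with the last time treated as an event. The reduction is 1 - 1.3/3.6 = 64% at 4 v 0 and 1 - 2.8/8.0 = 65% at 8 v 0 (53% to 83% over CV 0.4 to 0.7). It needs both retention and the change of estimator. Retention under the t-test removes 0%.

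**The case against.** The strongest reply is that the discard sentence does little harm to what section 10.0 specifies. Tests are named there only for healing time and the cosmetic outcomes, and a patient who leaves before healing can contribute to neither. This stands. A reader might infer that section 9.0 biases the primary comparison, or that keeping the data would by itself remove about 64% of the bias. The documents support neither: the omission comes from a t-test that needs an observed healing date. What the reply does not cover is the interim data, results observed before a late withdrawal, and the follow-up time that any better analysis would use.

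The two sections might also be read together, with data set aside under 9.0 and destroyed on request under 11.0. That softens the conflict, but the data set aside still reach no arm comparison. The consent pages were not available and may show which rule participants were promised.

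A reader might further infer that the discard rule covers patients terminated by the investigator. Section 9.0 does not say so; it is silent on their data. Nor need the loss be total: photographs are also stored in the medical record (section 6.0) and adverse events go to the IRB (section 8.0). No section returns either to the arm comparisons.

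Finally, the illustrated loss is one-sided or very unequal and reaches 20% of an arm. That is a fair criticism, and the figures are a scale rather than a forecast.

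**Conclusion.** The point holds in this limited form and should be fixed. The wording conflict is certain. The loss of interim, already observed and follow-up data follows directly if section 9.0 is applied as written. Its effect on the infection comparison cannot be sized, because the documents give no infection or withdrawal rate.

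The shifts of about -3.6 and -8.0 days belong to the complete-case t-test and rest on the assumed distribution, CV and selective loss. The direction is unknown: losing slow healers flatters an arm, losing fast healers does the reverse, and balanced loss gives about 0. A claim of inflated false positives in the pooled test is not supported, since the rate stays at or below about 5% in every scenario. That low rate partly reflects a pooled test that leaves the head-leg difference in its error variance, so it does not show that the estimate is unbiased.

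**What to change.** Reconcile sections 9.0 and 11.0 by replacing the discard wording in 9.0 with:

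> Data collected up to withdrawal are retained and analysed unless the participant asks for their removal (section 11.0).

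Match the consent form to it. Anyone enrolled under a promise to discard keeps that promise unless re-consented.

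Add to section 10.0:

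> All randomised participants with retained data, including those terminated by the investigator, are analysed in their assigned arm. Those not observed to heal are censored at their last assessment in a time-to-event analysis stratified by site. Withdrawals, terminations and removal requests are reported by arm and reason.

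The first change preserves the data; the second is what reduces the primary-outcome bias. If only the first is adopted, the primary result is unchanged for patients who leave before healing.

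The cost is a protocol amendment and a consent amendment. Data removed on request are still lost, though counted by arm. Censoring does not remove all the bias when withdrawal is related to healing: about -1.3 and -2.8 days remain in the illustration. The change has to be in place before any data are deleted.

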4.0 Inclusion/Exclusion Criteria

Inclusion Criteria:

- 18 years of age or older
- Post-operative wounds following Mohs surgery on the head or distal lower extremities
- Single Mohs post-operative defect
- Post-operative wounds greater than 1cm in width
- Depth of defect at least to subcutaneous tissue
- Patients have the ability to provide their own wound care
- Agreeable to regularly scheduled follow-up visits and transmission of photos via HIPAA compliant Vanderbilt University Medical Center Box
- Patients are able to provide informed consent

Exclusion Criteria:

- Under 18 years of age
- Unable to provide informed consent
- Unable to understand oral and written English
- Post-operative wounds not appropriate for secondary intention healing
- Sensitivity or allergy to APIS[®] biomaterial including collagen and its derivatives, porcine-derived materials or honey
- Immunosuppressed and organ transplant patients
- Post-operative wounds superficial to subcutaneous tissue

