6.0 Study Procedures

Arms and Interventions Two experimental groups

- 1) APIS[®] biomaterial on the head
- 2) APIS[®] biomaterial on the distal lower extremities

Two control groups

- 1) No intervention, standard SIH wound care on the head
- 2) No intervention, standard SIH wound care on the distal lower extremities

Experimental (40 patients): APIS[®] biomaterial. APIS[®] biomaterial placed on post-operative wound.

- 1) Head (20 patients)
- 2) Distal lower extremities (20 patients)
 - a. Device: APIS[®] biomaterial. This biomaterial was FDA cleared in 2019 for management of full and partial thickness wounds, pressure ulcers, venous stasis ulcers, diabetic ulcers, surface wounds, traumatic wounds, surgical wounds, abrasions, and donor site wounds.
 - b. One layer of APIS[®] will be applied to the post-operative wound covered by petrolatum impregnated gauze, a non-stick Telfa pad, gauze, and Opsite tape.

c. The biomaterial will be reapplied if it is completely absorbed at follow up and the wound depth below the epithelial level.

No intervention (40 patients): No APIS[®] biomaterial on post-operative wound.

- 3) Head (20 patients)
- 4) Distal lower extremities (20 patients)
 - a. Post-operative wound will heal via conventional secondary intention. Application of petrolatum impregnated gauze, a non-stick Telfa pad, gauze, and Opsite tape.

This study may be deemed complete prior to reaching above enrollment numbers if statistical significance is achieved or at the discretion of the research team.

Mohs Surgery – Day 0

Patients eligible for study will be offered opportunity to enroll. After informed consent has been obtained, the patient's clinical history, medical history, social history, medication history, and vital signs will be reviewed and documented. Pre and postoperative photos will be obtained and stored in the Electronic Medical Record and Vanderbilt HIPAA compliant Box.

Patients on day of surgery will be provided with a post-operative wound care instruction sheet (for both control and experimental groups). They will also receive a detailed instruction sheet for uploading post-operative photos to Vanderbilt's HIPAA compliant Box.

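### Section 9.0 lets an investigator who very likely knows the arm end study participation after randomisation, and nothing keeps such patients in follow-up or in the primary analysis

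*Combined protocol and SAP*

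**What the plan says.** Section 9.0 covers two ways out of the study. One is voluntary withdrawal, after which the participant's research data are discarded. The other is termination by the investigator: "Participants enrolled in the study may be terminated from the study at the investigator's discretion including but not limited to the following". Four grounds follow: loss to follow-up, "Nonadherence with wound care", "A participant's health status changes significantly which makes them not eligible for the study", and trauma to the wound. Nonadherence is not defined and has no threshold. What ends is participation in the study, and the section does not distinguish this from stopping the product.

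Four other sections bear on how this rule would work:

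- Section 4.0 lists as an exclusion "Sensitivity or allergy to APIS[®] biomaterial including collagen and its derivatives, porcine-derived materials or honey".
- Section 7.0 puts "Allergic reaction to APIS[®] biomaterial" first among the known and expected risks of the intervention.
- Section 6.0 gives the control condition as "No intervention (40 patients): No APIS[®] biomaterial on post-operative wound". For the other arm it says "The biomaterial will be reapplied if it is completely absorbed at follow up", provided that the wound still lies below the epithelial level.
- Section 2.0 has the only statement of masking: scar photographs "will be assessed by two blinded dermatologists using the VAS".

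Section 10.0 compares mean days to complete re-epithelialization with a Student's t-test. It defines no analysis population and gives no rule for a patient without a healing date.

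**The concern.** Randomisation makes the arms comparable at Day 0. They stay comparable only if leaving the study is unrelated to the combination of arm and outcome. Nonadherence, a change in health and wound trauma all occur after randomisation, and each may be connected with the treatment or with how the wound is healing. Section 9.0 lets the investigator act on them, or on grounds not listed, by ending participation.

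The investigator very likely knows the arm. The protocol never calls itself open-label, but it masks only the two photo raters, and the product is visibly applied, checked for absorption and reapplied. Wide discretion, undefined grounds and knowledge of the arm permit selective removal even when nobody intends it.

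The primary comparison is at stake, together with any infection, pain or scar outcome that falls after termination. A change of test alone would not repair this. If follow-up stops for reasons linked to treatment or slow healing, censoring in a time-to-event analysis would be informative too.

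**Working it through.** The plan gives no termination rate, dropout allowance, standard deviation, alpha or power, so there is no figure of its own to reproduce. The planned numbers agree with each other: 20 head + 20 leg = 40 per arm (section 6.0).

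**Step 1. What happens to a terminated patient.** The primary outcome is days from surgery to complete re-epithelialization (section 2.0). A patient terminated before healing has no such number. Section 9.0 provides no further follow-up and section 10.0 no rule for a missing value, so the t-test omits the patient by default.

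**Step 2. Whether the grounds can differ by arm.** Read together, sections 4.0, 7.0 and 9.0 allow a reaction to APIS to be taken as loss of eligibility. Controls receive no APIS, so in practice such a reaction would arise through APIS exposure. Section 9.0 does not name this ground. Nonadherence, trauma, loss to follow-up and general health change can occur in either arm.

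**Step 3. Shift in an arm mean.** Let the mean of all 40 patients be m, and let the n removed patients average m + D. The remaining mean is

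(40m − n(m + D)) / (40 − n) = m − nD/(40 − n).

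Both n and D are assumptions. D = 14 is one visit interval. D = 40 and D = 80 show how the shift scales.

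| Removed, n | D = 14 days | D = 40 days | D = 80 days |
|---|---|---|---|
| 1 | 14/39 = 0.4 | 40/39 = 1.0 | 80/39 = 2.1 |
| 2 | 28/38 = 0.7 | 80/38 = 2.1 | 160/38 = 4.2 |
| 4 | 56/36 = 1.6 | 160/36 = 4.4 | 320/36 = 8.9 |

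The formula is the same for either arm.

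**Step 4. Effect on the test.** A simulation with no true effect used 40 per arm, a two-sided 0.05 Student's t-test, 20,000 trials per scenario, and normal or lognormal outcomes (log-SD 0.5). All of these except the arm size and the test are assumptions. Patients were removed from the APIS arm only.

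| Removal rule | Removed | Mean shift (SD) | Type I error |
|---|---|---|---|
| At random | 1, 2 or 4 | about 0 | about 5% |
| From the slower-healing half | 4 | 0.08 | about 6% |
| The very slowest | 1 | 0.05–0.08 | 6–7% |
| The very slowest | 2 | 0.10–0.14 | 8–11% |
| The very slowest | 4 | 0.19–0.23 | 15–21% |

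When 4 are removed from the slower-healing half, false results favouring APIS rise from 2.5% to about 5%. The same removal from the control arm would mirror these results against APIS. The effect therefore depends on how strongly termination is tied to slow healing and on which arm loses the patients. The documents inform neither.

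**The case against.** The strongest reply is that the text does less than a suspicious reader might infer. Four stronger readings are tempting.

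- *One ground for termination can arise only in the APIS arm.* Section 9.0 does not name sensitivity to APIS. Its wording is permissive and speaks of a significant change in health, and nothing says that a local reaction to a dressing is one. The exclusion in section 4.0 also covers collagen, porcine materials and honey, so a control could be found sensitive through other exposure. Only a reaction to APIS itself is confined to one arm.
- *The bias favours APIS.* Most grounds apply to both arms. Section 1.0 describes wound care in secondary intention healing as burdensome and associates biologic dressings with fewer dressing changes. On that reasoning nonadherence could be commoner among controls. If nonadherent patients heal slowly, removing them would flatter the control arm.
- *Terminated patients' data are deleted.* The discard sentence concerns participants who choose to withdraw. Data already collected on a terminated patient are not said to be lost.
- *Reactions to the product would go unreported.* Section 8.0 sends all adverse events to the IRB and serious ones also to the manufacturer, and gives participants a pager number.

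These limits stand, and the point does not rely on any of the four readings. It is also fair that shifts of one or two days are small beside the 14-day visit interval and the healing gaps in section 1.0: 57 − 42 = 15 days for the head and 127 − 42 = 85 for the leg. What remains is that participation can be ended by discretion after randomisation, no follow-up is provided afterwards, and the primary test has no place for these patients.

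**Conclusion.** The point holds as a gap in design and analysis. Followed as written, section 9.0 can break the randomised comparison, because patients terminated before healing are absent from the section 10.0 test. That the investigator knows the arm is a strong inference and not a stated fact. That terminated patients drop out follows from the absence of any rule, since no sentence excludes them.

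The direction of the bias is undetermined, and its size cannot be estimated from the documents. The illustrations run from negligible, when removal is unrelated to healing, to a type I error of 15–21%, when the four slowest of 40 in one arm are removed. The second is a worst case and not a forecast. The case for changing the text is that the remedy is cheap, whereas the healing outcomes of terminated patients cannot be recovered once follow-up has stopped.

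**What to change.** In section 9.0:

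- State that eligibility is determined once, before randomisation.
- Replace investigator termination for changed eligibility, nonadherence, wound trauma or any other discretionary reason, including reasons under the open-ended wording, with this rule: the reason and date are recorded, and the participant continues the existing 14-day visits and the photo schedule to complete re-epithelialization unless consent is withdrawn.
- State that decisions about continuing the product are separate from leaving the study and rest with the treating clinician.

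In section 10.0:

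- Analyse all such patients in the arm to which they were randomised.
- Report discontinuations by arm and reason.
- Say how a patient who is truly lost, and so has no healing date, enters the analysis. Continued follow-up cannot solve that case.

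The cost is protocol wording and a few visits and photos that are already scheduled. The downside is that the comparison will include some patients not fully treated as assigned. That is the price of keeping the randomised groups intact.
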